### 7.2.2 Modified Cigarette Evaluation Questionnaire

The MCEQ [14] will be completed by the subject at V3, V7, V10, and V16.

The MCEQ consists of 12 items as presented in Table 6.

**Table 6: Modified Cigarette Evaluation Questionnaire - Questions and Subscales**

	Question	Subscale
1	Was smoking satisfying?	Smoking Satisfaction
2	Did cigarettes taste good?	Smoking Satisfaction
3	Did you enjoy the sensation in your throat and chest?	Enjoyment of Respiratory Tract Sensations
4	Did smoking calm you down?	Psychological Reward

**Table 6: Modified Cigarette Evaluation Questionnaire - Questions and Subscales**

	Question	Subscale
5	Did smoking make you feel more awake?	Psychological Reward
6	Did smoking make you feel less irritable?	Psychological Reward
7	Did smoking help you concentrate?	Psychological Reward
8	Did smoking reduce your hunger for food?	Psychological Reward
9	Did smoking make you dizzy?	Aversion
10	Did smoking make you nauseous?	Aversion
11	Did smoking immediately relieve your craving for a cigarette?	Craving Reduction
12	Did you enjoy smoking?	Smoking Satisfaction

Items are assessed on a 7-point scale, ranging from 1 (not at all) to 7 (extremely). Higher scores indicate greater intensity on that scale.

The subscales will be derived by averaging the individual non-missing item scores if at least 50% are non-missing, otherwise the subscale score will be set to missing.

### 7.2.3 Smoking History Questions

At V1, subjects will be asked 5 questions related to their current and past smoking behavior, shown in Table 7.

**Table 7: Questions on Smoking History/Habits**

	Question
1	Have you smoked for at least the past 10 years? (Yes/No)
2	How many years have you smoked?
3	On average, how many cigarettes per day have you smoked over the last year
4	On average, how many cigarettes per day have you smoked since you started smoking
5	On average, how would you describe your e-cigarette use over the last year? (Check one: Daily - How much use per day? / Weekly - How much use per week? / Sporadically [less than once per week] / Tried e-cigarettes. [between 1–10 uses] / Never tried e-cigarettes)

The smoking intensity is defined as the average number of CC smoked during the last year and will be derived from the self-reported subjects' answer to item 3. The smoking history intensity evaluating the amount a person has smoked over his/her life, expressed as number of pack-years, will be derived as: [item 2] x [item 4]/20.

## 7.2.4 Prochaska 'Stage of Change' Questionnaire: Intention to Quit Smoking

Subjects will complete the Prochaska 'Stage of Change' questionnaire at V1.

The Prochaska 'Stage of Change' questionnaire will be used to assess the smokers' mental state for the intention to quit (Precontemplation, Contemplation, Preparation, Action, and Maintenance). The details of the staging algorithm [15, 16] are provided in the Appendix 5 of the study protocol.

The questions are shown in Table 8.

**Table 8: Prochaska 'Stage of Change' Questionnaire**

	Question	Responses
1	Are you currently a smoker?	Yes No, I quit within the last 6 months No, I quit more than 6 months ago No, I have never smoked
2	In the last year, how many times have you quit smoking for at least 24 hours?	
3	Are you seriously thinking of quitting smoking?	Yes, within the next 30 days Yes, within the next 6 months No, not thinking of quitting

## 7.2.5 Intent to Use THS 2.2 Questionnaire

Subjects will be asked about their intention to use THS 2.2 using the Intent to Use THS 2.2 Questionnaire (ITUQ) at V4, V10, and at V16. This questionnaire consists of 7 items as presented in Table 9.

**Table 9: Intent To Use Questionnaire**

	Question	Responses
1	How likely or unlikely are you to use THS 2.2 regularly?	definitely not to definitely.
2	How likely or unlikely are you to use THS 2.2 and continue to smoke cigarettes? (*)	definitely not to definitely.
3	How likely or unlikely are you to use THS 2.2 and continue to use other tobacco-nicotine products besides cigarettes (such as nicotine patch, pipes, or chewing tobacco)? (*)	definitely not to definitely.
4	How likely or unlikely are you to use THS 2.2 to help you quit cigarettes? (*)	definitely not to definitely.
5	How likely or unlikely are you to use THS 2.2 rather than quitting cigarettes? (*)	definitely not to definitely.
6	How likely or unlikely are you to use THS 2.2 rather than use a product to help quit cigarettes (such as nicotine patches or nicotine gums)? (*)	definitely not to definitely.
7	How soon would you begin to use THS 2.2 regularly? (*)	Never Within a Week Within a Month Within 3 Months Within 6 Months More than 6 Months

\* Ask subjects who answer “to use THS 2.2” for item 1 with a different answer than “Definitely not”

Items are assessed on a 6-point scale, ranging from “definitely not” to “definitely” for the first 6 questions. Subjects will answer to items 2 to 7 only if they provide answer different from “definitely not” to item 1. Higher scores indicate greater likelihood to use the THS 2.2 product. Item 7 is rated on an ordinal scale, with 6 timeframe categories. For subjects who enter ‘Definitely not’ to item 1, they will be assigned ‘Definitely not’ to items 2-6 and ‘Never’ to item 7. Responses from items 1 to 6 will also be mapped into categories of ‘Positive intention’ (responses of “very likely” or “definitely”) and ‘Not positive intention’ (responses of “definitely not”, “very unlikely”, “somewhat unlikely”, or “somewhat likely”).

### 7.2.6 Product Preference Question

At V4, the following question will be asked to subjects prior to randomization (after the ITUQ questionnaire but prior to the question on the readiness of the subject to use the THS 2.2 for 26 weeks): “Which product would you prefer to be randomized to:” with

possible answers: THS 2.2 / CC / No preference. As an instruction to answer this question, subjects will be informed that their response will not influence the randomization process.

### 7.2.7 Socio-Economic Status Questionnaire

At V3, subjects will complete a series of questions related to their education, occupational status, size and annual income of their household. These data will be used to create measures of educational attainment (Low / Moderate / High) and annual household income (Low / Moderate/ High), as detailed in Table 10 below (see [17]).

**Table 10: Classification for the Socio-Economic Status Questionnaire**

Question	Answer	Category
Question 1. What is your highest educational level?	1 Less than High School	Low
	2 High School Graduate	Moderate
	3 Some High school or general education development (GED)	Moderate
	4 College Graduate	High
	5 Advanced Degree	High
Question 2. What is your current occupational status?	1 Working now	
	2 Only temporarily laid off, sick leave or maternity leave	
	3 Looking for work, unemployed	
	4 Retired	
	5 Disabled, permanently or temporarily	Not applicable
	6 Homemaker, keep housing	
	7 Student	
	8 Other	
Question 3. How many people are currently living in your household, including yourself?	Number (0-99)	Not applicable
Question 4. Of these people, how many are children under the age of 18?	Number (0-99)	Not applicable
Question 5. Of these people, how many are adults?	Number (0-99)	Not applicable
Question 6. Of the adults, how many bring income into the household?	Number (0-99)	Not applicable

**Table 10: Classification for the Socio-Economic Status Questionnaire**

Question	Answer	Category
Question 7. Which of these categories best describes your total combined family income for the past 12 months?	1 Less than \$10,000	Low
	2 \$10,000 to \$29,999	Low
	3 \$30,000 through \$44,999	Moderate
	4 \$45,000 through \$59,999	Moderate
	5 \$60,000 through \$74,999	High
	6 \$75,000 through \$99,999	High
	7 \$100,000 through \$149,999	High
	8 \$150,000 and over	High
	9 I do not know	< Missing>
	10 Prefer not to say	< Missing>

For Question 1 (Education) and Question 7 (Annual household income), if multiple answers are obtained the higher degree or income will be chosen; the subject cannot be classified if the answer is missing.

Education and income categories will be combined to create a composite measure for socio-economic status (SES) with categories defined as follows:

- Low (Low education and Low income categories)
- Moderate (Low income and Moderate education, Low income and High education, Moderate income and Low education, and High income and Low education)
- High (Moderate income and Moderate education, Moderate income and High education, High income and Moderate education, and High income and High education).

Respondents who do not report either income or education will be excluded from the analysis of the composite SES.

### 7.2.8 Cough Questionnaire

Subjects will self-report the respiratory symptom ‘cough’ using a visual analog scale (VAS), three Likert scale questions, and one open ended question at V3, V7, V10, and V16.

Subjects will be asked if they have experienced a regular need to cough, (*i.e.*, whether they have coughed several times in the previous 24 hours prior to assessment). If the answer is ‘yes’, subjects will be asked to complete the questionnaire.

The VAS will assess how bothersome cough is to the subject ranging from ‘not bothering me at all’ to ‘extremely bothersome’, and this will be given a numeric value between 0 and 100, measured on a 100 mm scale.

Subjects will also be asked to assess the intensity and frequency of cough and the amount of sputum production on Likert scales as presented in Table 11.

**Table 11: Cough Assessment Likert Scales**

	Question	Likert Scale
1	The intensity of cough	1 = very mild 2 = mild 3 = moderate 4 = severe 5 = very severe
2	The frequency of cough	1 = rarely 2 = sometimes 3 = fairly often 4 = often 5 = almost always
3	The amount of sputum production	0 = no sputum 1 = a moderate amount of sputum; 2 = a larger amount of sputum; 3 = a very large amount of sputum.

## 7.2.9 Lifestyle Assessment

Subjects will be asked questions to capture baseline covariates to assess lifestyle characteristics at V3. The replies to the questions reported in Table 12 will be considered for their inclusion in the analysis as described in Section 4.1.4 “Covariates for Smokers’ Health Profile Analysis”.

**Table 12: Lifestyle Assessment Questions**

	Question	Answers
1	How many times per week do you eat fast food? (e.g., hamburgers, hot dogs, pizza, french fries)	Number (0-99)
2	How many alcoholic drinks do you have a day?	Number (0-99)
3	How many times a week do you exercise?	Number (0-99)
4	What is the average duration of each exercise session? (record in minutes)	Number (0-999)
5	How many nights per week do you sleep less than 6 hours?	Number (0-9)
6	Do you live in a household with one or more smokers, other than yourself?	Yes/No

The total weekly exercise time (minutes/week) will be in general derived as [item 3]x[item 4] of the Lifestyle assessment questions. Subsequent to data review findings, the following derivation rules will also be applied:

- If the result is greater than 3360 minutes (corresponding to an average daily exercise time of 8 hours) then the total weekly exercise time is set to 3360 minutes.
- If the reply to item 3 is missing the total weekly exercise time is missing, apart from when item 4 is zero which results into a total weekly exercise time equal to zero. Similarly, if the reply to item 4 is missing the total weekly exercise time is missing, apart from when item 3 is zero which results into a total weekly exercise time equal to zero.

## 8 SAMPLE SIZE JUSTIFICATION

The sample size for this study was defined based on the sample size requirements of the original study, for which the sample size was calculated to ensure an overall study power of at least 90%, while maintaining at least 80% power to detect the expected effect of THS 2.2 as compared to CC for each individual endpoint of the “smokers’ health profile”, over 26 weeks of exposure. This required 475 subjects randomized per group accounting for an anticipated 75% of the THS 2.2 arm to be Mostly THS 2.2 users (i.e. report at least 70% THS 2.2 use).

Based on the assumptions that 30% of the 950 subjects will not be enrolled or will drop out from the extension study and a potential decrease from 75% to 50% of Mostly THS 2.2 users among subjects randomized to THS 2.2, the study will have at least 90% probability to determine the effect of THS 2.2 as compared to CC on FEV1 at V16 with a margin of error (95% CI) of at most  $\pm 1.5$  %pred. The anticipated SD of 6.4 %pred was estimated using the results of the “Lung Health Study” [1].

Following our current understanding of product use data in the main study, the definition of the product use categories was redefined and the underlying assumptions re-evaluated so that approximately 60% of the subjects in the THS 2.2 arm are expected to be in the THS-use category, with an anticipated 20% of subjects drop-out or reporting insufficient product use data in the two arms of the main study. Based on the 65% rate of enrollment into the extension study observed among subjects randomized in the main study, the extension study will have more than 90% probability to determine the effect of THS-use compared to CC-use on FEV1 at V16 with a margin of error (95% CI) of at most  $\pm 1.5$  %pred.

## 9 CHANGES FROM THE PROTOCOL SPECIFIED STATISTICAL ANALYSIS

The following changes from the protocol specified statistical analysis were identified prior to database lock:

- Additional endpoints collected in the study but not listed in Section 3 of the protocol are reported in Section 5.3 “Additional Endpoints”. This includes residual volume which was not included in the protocol objectives but will be derived for interpretation of lung volume. Also, the Apo B/Apo A1 ratio will be analyzed and results will be used for the interpretation of Apolipoprotein data. The quantity excreted in 24h will be derived from the laboratory for Albumin as additional risk marker associated with CVD and renal disease. Spirometry (clinical interpretation and COPD categories), Respiratory symptoms (cough assessment VAS and Likert scales), and Body weight and BMI were not detailed as safety endpoints in Section 3 (Study Objectives) of the protocol but were considered for safety analysis in Section 12.6.4 of the protocol and are analyzed accordingly, in line with analyses from the original study.
- The definition of safety periods in Section 12.6.4 of the protocol showed that V3 is included in the Screening period and excluded from the Product trial period. However, in line with emergent events starting at enrollment, V3 is now excluded from the Screening period and included with the Product trial period instead.
- The distribution of product use cross-tabulation summary outlined in Section 12.7.2.1 will be summarized over the entire 12 month exposure period across the main and extension studies rather than the 6 months specified in the protocol.
- Clarified in Section 10.1 which visits are included in FAS-AR definition.
- The analysis of cough symptoms specified in Section 12.6.2 of the protocol was updated to present odds ratios rather than incidence rate differences because of use of the logistic model. The original model using the identity link to provide incidence rate differences could lead to convergence issues and so the approach was changed. In addition, age and smoking intensity were included in the logistic model, for consistency with the model used for other endpoints. Also, p-values will not be calculated.
- Inferential analyses in Sections 12.7.1, 12.7.2, and 12.7.3 will be presented at Months 3 and 6 in addition to Month 12.

- As noted in Section 10.2, the FAS-EX analyses of primary and secondary endpoints will be performed using 6-month product use categories for Month 1 – Month 6 data and 12-month product use-categories for Month 7 – Month 12 data rather than using the 12-month product use categories for all timepoints as planned in the protocol, to allow for consistency with the results in the original study.

## 10 ANALYSIS POPULATIONS

The Full Analysis Set – as Exposed (FAS-EX) will be the primary analysis set for clinical risk endpoints, BoExp, and questionnaires, based on the overall product use pattern categories. Supportive statistical considerations are reported in Appendix 16.2.

Supportive analysis will be run on the Per Protocol (PP) population and a sensitivity analysis will be conducted on the Full Analysis Set – as Randomized (FAS-AR).

The primary population for the assessment of safety will be the Safety population. Safety will be summarized and presented by randomization arm and according to product use pattern categories.

### 10.1 Full Analysis Set - As Randomized (FAS-AR)

The FAS-AR consists of all the randomized subjects with signed ICF who have both a valid baseline and at least one valid post-randomization value for one of the primary endpoints collected at V7, V10, or V16.

Subjects enrolled at sites that are terminated due to findings of non-compliance with good clinical practice (GCP) and/or with the protocol will be excluded from the FAS-AR.

Subjects included in the FAS-AR are analyzed as per randomized arm.

### 10.2 Full Analysis Set - As Exposed (FAS-EX)

The FAS-EX consists of all subjects in FAS-AR who have at least one record of reported product use diary post randomization.

The exposure assignment for the FAS-EX will be actual product exposure as explained in Section 4.1.2 “Definition of Product Use Pattern Categories”. In particular, the analysis on FAS-EX will be conducted using time-varying product use categories, where Month 1 – Month 6 will be analyzed using product use categories defined for ]V4, V10[, and Month 7 – Month 12 data will be analyzed using the product use categories defined for ]V4, V16[.

### 10.3 Per Protocol Population

The PP population is a subset of the FAS-EX and includes all randomized subjects who:

- Are subjects randomized to THS 2.2 who have a product use pattern category of THS-use or are subjects randomized to CC who have a product use pattern category of CC-use.
- Were included in the PP population in the original study.
- Do not make a quit attempt (see Section 6.3.3 “Adherence to Product Allocation”).
- Have no major protocol deviation that impacts the overall subject evaluability (see Section 11.1 “Major Protocol Deviations”).
- Have data for at least one endpoint of the “smoker’s health profile” which is not missing or excluded from the PP analysis at V7, V10, or V16, because of a major protocol deviation on product adherence and diary adherence (see Section 6.3.3 “Adherence to Product Allocation”) impacting evaluability (See Section 11.1 “Major Protocol Deviations”).

Subjects included in the PP population are analyzed as per randomized arm.

### 10.4 Safety Population

The Safety population consists of all the subjects enrolled with signed ICF who have at least one valid value for a safety assessment. This analysis set excludes all subjects enrolled in sites terminated due to findings of non-compliance with GCP and/or with the protocol. In general, the exposure assignment for the Safety population will be by randomization arm and according to the product use pattern categories (J[V4, V16]) as defined in Section 4.1.2 “Definition of Product Use Pattern Categories”.

## 11 PROTOCOL DEVIATIONS

Protocol deviations are defined as deviations from any procedure defined in the Study Protocol, including but not limited to, as any violation of inclusion/exclusion criteria, mis-randomizations, assessments not performed according to protocol restrictions, or use of drugs that are known to affect the component of the “smokers’ health profile”.

Information following site monitoring and other reviews will be documented in the site visit reports, follow-up letters, audit documentation, or other manual review and subsequently recorded in an electronic data capture (EDC) system. Additional protocol deviations may be identified in the data review, these will also be recorded in the EDC system or imported into Study Data Tabulation Model (SDTM) datasets.

All deviations will be reviewed to determine their impact when subjects are assigned to analysis populations. Each deviation will be classified as major or minor; all major deviations will be further reviewed to determine whether or not the deviation impacts the evaluability of the results and therefore should result in the subject being excluded from the PP population.

### 11.1 Major Protocol Deviations

Subjects with major protocol deviations will be identified to determine whether they will be excluded from any of the analysis populations.

The categories for the major deviations may include, but are not limited to the deviations presented in Table 13.

**Table 13: Definition of Major Protocol Deviations**

Category	Description
Mis-randomization	Being administered the wrong product according to the randomization schedule or being randomized with an incorrect stratification variable.
Product misallocation	Subjects randomized to CC who had access to THS 2.2.
Product adherence	Non-adherence in the THS 2.2 arm during period ]V4, V7], ]V7, V10[ or ]V10, V16[ is defined based on the reported product use as any of the following occurrence: - Use of more than 5 CC in a single day during the period. - Average THS 2.2 use is less than 70% of total THS 2.2 and CC use.
Entry Violation	Violation of inclusion/exclusion criteria.
Diary adherence	If less than 75% of the daily product use assessments over the period ]V4, V7], ]V7, V10[, [V10, V16[ are available, or product use data is missing over a period of more than 7 consecutive days.
Duration of 24 hour collection	Total urine collection covering a period of less than 23 hours and more than 25 hours for assessments at Baseline, V7, V10, or V16, including significant missing collections within the 24 hour sample.

Among the above criteria, violations of inclusion criteria 1 or 2, or exclusion criteria 2, 16, 17, 19 or 21 of the original study or violation of the extension inclusion criterion 2 or exclusion criterion 4 will be considered as impacting the evaluability. Duration of 24h urine sample may be considered as not impacting the evaluability if collected at V7 or V10, or if collected over a period of at least 4 hours. The other criteria will be assessed for their impact on the PP population and evaluated during the pre-analysis data review meeting (Section 6.3.1 “Methods of Assigning Subjects to Product Arms”).

All major protocol deviations related to the original study and impacting evaluability will impact the overall subject evaluability leading to the exclusion from the PP population, apart

from those related to product adherence and diary adherence. Following major protocol deviation of product adherence or diary adherence impacting evaluability in period ]V4,V7], all non-safety data at V7 will be flagged and excluded from the descriptive summaries and analysis for the PP population. The same approach will be used for descriptive summaries and analysis at V10 following a major protocol deviation of product adherence or diary adherence impacting evaluability in the ]V7, V10[.

All protocol deviations occurring during the extension study and categorized as major and impacting evaluability will not directly impact the overall subject evaluability, however all non-safety data at Month 7 to Month 12 will be flagged and excluded from the descriptive summaries and analysis for the PP population.

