7.6.2 Urine Samples

Spot urine samples will be used for urine pregnancy test and safety urine analysis for each visit.

24-hour urine collection: the day before the visit, subjects will start collection of his/her 24-hour urine. Subjects will discard their first void in the morning. The collection period will start immediately after. After 24-hours \pm 1h of urine collection, subjects will empty their bladder again in the morning of the visit and this urine will be used as the final portion of the 24-hour urine sample. During the collection period, all urine passed must be collected and put into the sampling container. No urine should be passed into the toilet. The start and the end time of

Confidentiality Statement

Data and information contained in this document are considered to constitute trade secrets and confidential commercial information, and the legal protections provided to such trade secrets and confidential information are hereby claimed under the provisions of applicable law. No part of this document may be publicly disclosed without the written consent of Philip Morris Products S.A.

urine collection will be recorded by the subject and checked by the site staff. The volume of 24-hour urine will be measured by the site staff upon collection of urine containers from the subjects. For assessment of urine BoExp, creatinine, 8-epi-PGF_{2α} and 11-DTX-B₂, albumin, and for sample biobanking, aliquots from the 24-hour urine collection will be taken. In the schedule of events (Appendix 1) for the 24-hour urine collection, the dot corresponds to the day on which the 24-hour urine collection period ends.

The 24-hour urine collection will be collected according to Appendix 1

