## 7.1 Clinical Risk Endpoints and Biomarkers of Exposure

### 7.1.1 Clinical Risk Endpoints and Biomarkers of Exposure in Urine

The adjustment for creatinine of the urinary clinical risk endpoints and biomarkers will be calculated as:

Clinical Risk Endpoint or Biomarker (adjusted for creatinine )

$$= \frac{[\text{Clinical Risk Endpoint or Biomarker}]}{[\text{Creatinine}]}$$

where the [ ] indicated concentrations measured from the same 24 hour urine collection.

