**Table 15: Assessment Windows**

Assessment	Nominal Time point(s)	Window
24-hour urine collection	V3, V7, V10, and V16	Start collection in the morning of the day prior to the visit, end after 24 ± 1 hours since the starting time
Ambulatory Visit	From V1 to V2	Not more than 42 days
	From V2 to V3	Not more than 5 days
	From V3 to V4	8 days ± 2 days
	From V4 to V5, and subsequent monthly visits	± 5 days with respect to the planned visit date.

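### SAP 11.1 lets urine collections as short as 4 hours be waived without a stated reason, and a V16 duration deviation that is not waived excludes non-urinary endpoints from the per-protocol analysis

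*SAP*

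**What the plan says.** **Window.** Protocol 7.6.2 asks for 24 hours within one hour either way and states: "During the collection period, all urine passed must be collected and put into the sampling container". SAP Table 15 repeats the window. SAP 7.1.1 forms each urinary endpoint as a ratio to creatinine, using "concentrations measured from the same 24 hour urine collection".

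**Deviation.** SAP Table 13 lists as major: "Total urine collection covering a period of less than 23 hours and more than 25 hours for assessments at Baseline, V7, V10, or V16". Significant gaps within the sample are included but not defined.

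**Waiver.** The text below Table 13 says the duration "may be considered as not impacting the evaluability if collected at V7 or V10, or if collected over a period of at least 4 hours". Other criteria go to a pre-analysis data review meeting. The cross-reference given for that meeting is SAP 6.3.1, which covers arm assignment and contains no evaluability criteria.

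**Consequence.** There are two rules, both for PP only:

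- Original study: a major deviation impacting evaluability takes the subject out of PP. Only product adherence and diary adherence are exempt.
- Extension study: a deviation "categorized as major and impacting evaluability will not directly impact the overall subject evaluability", but "all non-safety data at Month 7 to Month 12 will be flagged and excluded from the descriptive summaries and analysis for the PP population".

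**Analysis sets.** SAP 10 makes FAS-EX primary and PP supportive. SAP 10.1 and 10.2 set no urine-duration condition for FAS-AR or FAS-EX.

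**The concern.** Two features of the rule pull in different directions.

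First, the waiver is wide. If it is used to its full extent, a near-spot V16 sample can be set against a full 24-hour Baseline sample for the same subject. This affects 11-DTX-B2, 8-epi-PGF2α and total NNAL among the primary endpoints, and total NNN and Neq among the secondary ones. Dividing by creatinine corrects for dilution. It does not correct for which part of the day was sampled relative to product use. No planned analysis would show whether this matters.

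Second, when a collection is judged to impact evaluability, the exclusion is wider than the problem. The length of a urine collection has no bearing on spirometry or on a blood draw, yet the rule works by visit or by subject and not by endpoint. Valid values for unaffected primary endpoints are then dropped from the PP analysis, which is one of the analyses meant to support the primary result.

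**Working it through.** The plan states no figure to reproduce here. The check is a reading of the rules plus short arithmetic.

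**1. Window.** SAP Table 15 says a collection should "end after 24 ± 1 hours since the starting time". So 24 − 1 = 23 h and 24 + 1 = 25 h, which match the limits in Table 13. As printed, Table 13 joins them with 'and', and no collection is both shorter than 23 h and longer than 25 h. Given Table 15 and Protocol 7.6.2, 'or' is plainly meant.

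**2. Size of the waiver.** 4/24 = 0.167, or 17% of the planned period. 4/23 = 0.174, or 17% of the shortest collection inside the window. The waiver has no upper limit, so collections over 25 h also qualify.

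**3. What each case leads to.** Durations are illustrative.

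| Collection | Major? | Waiver available? | If judged to impact evaluability (PP only) |
|---|---|---|---|
| Baseline, 10 h | yes | yes (at least 4 h) | whole subject leaves PP |
| Baseline, 3 h | yes | no | whole subject leaves PP |
| V7 or V10, any length outside 23–25 h | yes | yes (visit) | whole subject leaves PP |
| V16, 10 h | yes | yes (at least 4 h) | all non-safety Month 7–12 data leave PP |
| V16, 3 h | yes | no | all non-safety Month 7–12 data leave PP |

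The last column needs a positive judgement in every row. If the waiver is applied wherever it is available, only collections under 4 h at Baseline or V16 can have any consequence. How it applies to samples with significant gaps is not stated.

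**4. Primary endpoints by source** (Protocol 3.1, 7.3.5.1, 7.4 and 7.5.1):

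- Urine: 11-DTX-B2, 8-epi-PGF2α, total NNAL (3 of 8).
- Not urine: FEV1, HDL-C, sICAM-1, COHb, WBC (8 − 3 = 5 of 8).

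WBC is read from the safety haematology panel, so whether it counts as non-safety data is open. The rule therefore reaches four non-urinary primary endpoints clearly, and a fifth possibly.

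**5. Loss in PP.** The documents give no rate of duration deviations, so the number of PP values lost cannot be computed. For scale only, suppose a fraction f of V16 PP values were dropped. The standard error at V16 would grow by about 1/√(1 − f):

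- f = 5%: 1/√0.95 = 1.026
- f = 10%: 1/√0.90 = 1.054
- f = 20%: 1/√0.80 = 1.118

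These fractions are assumptions without support in the documents, and step 3 suggests the true value is lower. The factor is also close to an upper bound, because the repeated-measures model keeps the subject's V7 and V10 values.

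**The case against.** The case against making much of this is fair in several respects.

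- **The waiver is permissive, not automatic.** A reader might infer that a 5-hour V16 collection must be kept and a 3-hour one must be removed. The SAP mandates neither. SAP 11 sends every major deviation to further review, and SAP 13.4 places the data review before database lock.
- **Being a deviation is not enough.** A reader might infer that any out-of-window collection removes FEV1 and the blood markers. Removal needs a deviation that is both major and impacting evaluability.
- **Only PP loses data.** FAS-EX and FAS-AR keep the non-urinary endpoints, and after a V16 deviation the subject's V7 and V10 data stay in PP.
- **The two complaints offset each other.** The looser the waiver, the rarer the exclusion. A large PP loss is not a supported inference.
- **Bias in the urinary endpoints is not shown.** They are concentration ratios and depend less on complete collection than a 24-hour total would. Nothing in the documents measures variation within the day. A reader might point to 24-hour albumin, where an unscaled 4-hour volume would give a value 24/4 = 6 times too low. But SAP 12.7.2.4.1 only lists that quantity, and SAP 9 does not say how the laboratory derives it.
- **Dropping a whole visit keeps one common evaluable set.** That is a legitimate preference.

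All of this limits the size of the problem. It does not supply a reason for 4 hours, give FAS-EX any check on collection length, or explain why urine timing should exclude a spirometry result. SAP 10.1 does ask for valid values, but it attaches no duration criterion and sets membership of the population, not the use of a particular urine result.

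**Conclusion.** The point holds as a modest correction. SAP 11.1 allows, at the reviewers' discretion, a collection of about one sixth of the planned length (or any length at V7 or V10) to count as evaluable, with no reason given. The primary analysis of three of eight primary endpoints has no duration check. A V16 urine-duration deviation judged major and impacting evaluability excludes FEV1, HDL-C, sICAM-1 and COHb from PP along with the urinary endpoints; for WBC the text is unclear.

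The documents do not support reading this as a threat to the primary analysis of the non-urinary endpoints, which FAS-EX retains, or as evidence that the urinary results are biased. The PP loss cannot be quantified and is probably small. That judgement assumes that the waiver is used broadly, so that mainly collections under 4 hours have any consequence. The wording in Table 13 is clerical.

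**What to change.** 1. In SAP 11.1, state that an extension-study urine-duration deviation excludes from PP only the urine-derived endpoints at that visit: 11-DTX-B2, 8-epi-PGF2α, total NNAL, total NNN, Neq and urinary albumin. Blood, breath and lung-function data stay in, which also settles WBC for this deviation. Baseline exclusions cannot be fully reversed here, because SAP 10.3 requires membership of the original study's PP population.
2. Add one FAS-EX sensitivity run of the three urinary primary endpoints, total NNN and Neq, restricted to collections of 23 to 25 hours at Baseline and at the analysed visit. This tests directly whether admitting shorter or longer collections matters. Start and end times are already recorded (Protocol 7.6.2), and SAP 12.7.1.3.7 already plans a FAS-EX run of similar scale for creatinine values below the quantification limit.
3. As an editorial correction, change 'and' to 'or' between the two limits in Table 13.

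The cost is SAP wording and one extra table. The restricted run will have fewer urinary values and so wider intervals.
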